During Session 1, which will occur using the HIPAA-compliant version of Zoom the full consent & assent process will take place with parent & youth completing forms via REDCap. All youth who complete the TSST will have a full Session 1, while families whose youth merely attend as support will be given the study description by email or phone, and will be sent a link to REDCap for signing consent/assent. Parents will supply background information on family income, education and composition. Parents and the youth will complete the MacArthur Health and Behavior Questionnaire items for the Internalizing, Externalizing and ADHD scales, and reports of pubertal development. Youth will complete the Network of Relationships Questionnaire and other similar surveys in which they respond to questions about their relationships with their parents, their friend, and peers in general. Session 2 occurs approximately 2 weeks after Session 1. If the youth is in the one of the close friend conditions, their same sex close friend will also accompany them online. If they are in the unfamiliar peer condition, an unfamiliar peer of the same age and sex will be recruited and arrive online for session 2, likely with their parent. The TSST involves developing and delivering a speech and doing mental arithmetic while being judged/evaluated by two judges while being filmed over HIPAA-compliant Zoom. We will collect saliva for cortisol and alpha amylase assessment. Breakout rooms will be used in Zoom to create the different environments described below. For example, the session will start with a friendly experimenter who guides people through the online session, and participants will be sent to breakout rooms to either wait their turn or engage in the TSST task, and return to the main room with the friendly experimenter. We have successfully used this procedure in a recent study nearly identical to this one, with the exception of the Peer conditions.

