There are four conditions in this experiment: Close Friend Who Also Completes the TSST, Close Friend Provides Social Support, Unfamiliar Peer Who Also Completes the TSST, and No Partner. The Close Friends and Unfamiliar Peer will complete the Network of Relationships Questionnaire and similar surveys about their relationship with the Target youth (Close Friend Conditions) or their own same sex best friend (Unfamiliar Peer). Both Close Friends and Unfamiliar Peer who complete the TSST will undergo the same procedures as the Target Child during session 2,

PROTOCOL TITLE: Does Social Buffering Continue to be Effective Over the Peripubertal Period
When Friends Share the Stressor Experience?

VERSION DATE: v.3.3 3.31.23

including salivary measures. Thus, we will have 50 boys and 50 girls who undergo the same procedures in parallel with the Target youth. We will have an additional 25 boys and 25 girls who provide social support but do not go through the same procedures.

5.2 Study Procedures:

200 target children, 11- 14 years of age will be tested in one of four conditions: 1) Close Friends Both Tested, 2) Unfamiliar Peers Both Tested, 3) Close Friend Gives Support, and 4) No Social Support.

Social Buffering Manipulations: Will include 4 between-subjects conditions and both sexes. Participants will be randomly assigned to Close Friend-Both Tested, Unfamiliar Peer-Both Tested, Received Support from Close Friend, and No Social Partner conditions. Definition of Close Friend. We will ask the parent to have the child select the close same-sex friend they want to have accompany them online. The parent then has to contact that child's family and get their permission for us to contact them. We have successfully conducted studies in which the child brings their best friend.

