8.0 Study Population

8.1 Inclusion Criteria: Healthy 11-14 year olds. Additional inclusion criteria are imposed in ensure that youth will be able to follow the study procedures, sufficient vision, hearing, and language skills to provide verbal and written assent, see and read stimuli presented on the computer screen, and hear verbal instructions provided by the experimenter and judges.

8.2 Exclusion Criteria: Premature birth (less than 37 weeks), congenital and/or chromosomal disorders (e.g. cerebral palsy, FAS, mental retardation, Turner Syndrome, Down Syndrome, Fragile X), Autism Spectrum Disorders, history of serious medical illness (e.g., cancer, organ transplant), serious psychiatric illness, or youth taking systemic glucocorticoids or beta-adrenergic medications.

8.3 Screening: Screening will occur by asking parents questions at the time of recruitment. To reduce confounding age and pubertal stage, we will use a stratified recruitment method. During recruitment, parents will be asked 3 questions about their child's physical development, and children will be initially categorized into Pre/Early and Mid/Late Puberty. As cells fill, participants will no longer be enrolled into those cells. Also, to increase minority representation we will also sample across zip codes with higher racial and ethnic minority representation.

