10.0 Local Number of Participants

PROTOCOL TITLE: Does Social Buffering Continue to be Effective Over the Peripubertal Period
When Friends Share the Stressor Experience?

VERSION DATE: v.3.3 3.31.23

10.1 Local Number of Participants to be Consented: We plan to analyze at least 200 target participants. Of those 50 will participate alone, while 150 will participate with a social peer. Social peers will be enrolled as they will at least complete a questionnaire. Thus, we will enroll at least 350 children. To account for attrition between sessions/replacement for incomplete data, we anticipate up to 400 children may be enrolled.

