14.0 Statistical Considerations

14.1 Data Analysis Plan: 200 primary participants, including 100 females and 100 males. Within each group there will be 50 early and 50 late puberty participants.

Study Design. This randomized control study will assign study participants into one of four conditions: Close friend both tested, Unfamiliar Peer both tested, Received support from close friend who is not tested, and no partner. To perform the randomization, participants will first be placed into one of four groups based on sex and pubertal stage: early puberty, female;

PROTOCOL TITLE: Does Social Buffering Continue to be Effective Over the Peripubertal Period
When Friends Share the Stressor Experience?

VERSION DATE: v.3.3 3.31.23

late puberty, female; early puberty, male; and late puberty, male. Next, participants within a group will be randomly assigned to one of four conditions equally in order to have a balanced design. Pubertal stage will then be treated as a continuous variable.

Statistical Methods

Preliminary Analyses to Determine Covariates Need for Primary Analyses. The purpose of collecting data on potential covariates is to identify variables that are correlated with both the independent variable (social buffering condition, sex, pubertal stage) and the primary outcome measures. Those covariates that are associated with the independent and outcome variables will be controlled for in the primary analyses. Those that are not will be used to describe the sample, but will not need to be included in the analyses to obtain unbiased estimates. For each potential covariate (listed as “other type” in section 4.3, Outcome Variables), we will conduct correlations or t-tests with pubertal stage, and t-tests, ANOVAs, or chi-square tests (as appropriate) with sex and condition. If data do not confirm to modeling assumptions, we will use non-parametric analogs instead.

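### An obtainable close friend is not required before randomisation but is needed in two of the four conditions; with sessions converted to alone and no as-randomised rule, the arms can differ for reasons other than the partner

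*Combined protocol and SAP*

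**What the plan says.** Entry and assignment:

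- Section 8.1 admits "Healthy 11-14 year olds" with adequate vision, hearing and language. Section 8.2 lists medical and psychiatric exclusions. Neither mentions a friend.
- At screening (8.3), "parents will be asked 3 questions about their child's physical development", to place the child in a pubertal group. Nothing is asked about a friend.
- In 14.1, after grouping by sex and pubertal stage, "participants within a group will be randomly assigned to one of four conditions equally in order to have a balanced design". Friend availability is neither a stratum nor a precondition.

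Partner requirements:

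- Section 5.1: "If the youth is in the one of the close friend conditions, their same sex close friend will also accompany them online". In the Unfamiliar Peer condition the study finds the partner; No Partner needs nobody.
- Section 5.2: "We will ask the parent to have the child select the close same-sex friend they want to have accompany them online". The parent must then approach the other family and "get their permission for us to contact them". A note later in 5.2 requires the friend to be within two years of the target's age.
- Section 11.1 adds consent from the friend's parent through a REDCap link, with a reminder call. If consent is not in hand before the online session, the session becomes an alone session. Section 19.5 repeats this.

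Numbers and analysis: section 10.1 plans 50 targets alone and 150 with a peer, and adds: "To account for attrition between sessions/replacement for incomplete data, we anticipate up to 400 children may be enrolled". Sections 14.1 to 14.4 do not say whether a converted youth is analysed in the assigned or the tested condition.

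**The concern.** Randomisation makes the four groups comparable at the moment of assignment. Here a further requirement applies afterwards, in two groups only: a nameable friend of suitable age and a family that agrees in time. A youth who cannot meet it does not receive a friend condition; the same youth assigned to Unfamiliar Peer or No Partner is tested as planned.

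The conversion rule adds to the asymmetry. If converted sessions are counted as alone, the failures leave the friend arms and collect in the comparison arm.

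Youth without an obtainable friend may respond differently to social evaluation. The protocol allows for this: it treats relationship quality, peer acceptance and victimisation as possible covariates (5.2). If such youth have the larger responses, friend arms look calmer than they should. That could pass for buffering where both friends are tested, and could mask the increase the investigators predict where the friend only gives support. If they have smaller responses, the errors run the other way. Every friend versus non-friend contrast is exposed.

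**Working it through.** **The plan's own count.** Four conditions of 50 give 4 × 50 = 200 targets; 50 alone + 150 with a peer = 200; 200 targets + 150 partners = 350 children. This agrees with 10.1. The count has no line for friend failures or conversions.

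**When the friend requirement acts.** No sentence dates friend selection relative to randomisation. Section 5.1 makes the friend's attendance conditional on already being in a friend condition, and 11.1 converts a session that was a friend session. Together they imply that the requirement acts after assignment.

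**Size if analysed as tested.** Assumed inputs, absent from the documents: *q*, the share of targets whose friend cannot be obtained, and *g*, the mean AUCi difference in SD units between those youth and the rest. All failures are treated as converted to alone, none are replaced, *q* is the same in both friend arms, and there is no true friend effect.

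- Friend arms: 100 assigned, 100(1 − *q*) remain, none of them failures.
- Unfamiliar Peer: a share *q* are youth of the failing kind. Spurious difference from the friend arms = *q* × *g*.
- No Partner: 50*q* such youth by randomisation plus 100*q* converted, among 50 + 100*q*. Spurious difference = *g* × 150*q* / (50 + 100*q*).

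With *g* = 0.5 SD:

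| *q* | Each friend arm | Alone | Share of such youth in Alone | Bias vs Unfamiliar Peer | Bias vs No Partner |
|---|---|---|---|---|---|
| 5% | 47.5 | 55 | 7.5/55 = 14% | 0.025 SD | 0.07 SD |
| 10% | 45 | 60 | 15/60 = 25% | 0.05 SD | 0.125 SD |
| 20% | 40 | 70 | 30/70 = 43% | 0.10 SD | 0.21 SD |
| 30% | 35 | 80 | 45/80 = 56% | 0.15 SD | 0.28 SD |

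At *q* = 20%, letting *g* run from 0.2 to 0.8 SD gives 0.04 to 0.16 SD against Unfamiliar Peer and 0.09 to 0.34 SD against No Partner.

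**Effect on false positives.** For the two friend arms pooled against Alone, unadjusted, two-sided 5%, with SD 1:

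- *q* = 10%: standard error √(1/90 + 1/60) = 0.167; shift 0.125/0.167 = 0.75; type I error about 12%.
- *q* = 20%: standard error √(1/80 + 1/70) = 0.164; shift 0.214/0.164 = 1.31; type I error about 26%.
- *q* = 5%: about 7%.

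Pooled friend arms against Unfamiliar Peer give about 5%, 6% and 9% at *q* = 5%, 10% and 20%.

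**Size if analysed as randomised.** All four groups keep the same mix, so this bias is absent. The cost is dilution: if converted youth get no friend effect, the friend versus No Partner difference shrinks by the factor (1 − *q*), to 80% of its value at *q* = 20%.

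**The case against.** The strongest reply is that the plan already deals with a missing friend. Conversion keeps the youth in the trial with an outcome, and an as-randomised analysis would then be free of this bias. That is correct, and it is why the missing analysis rule matters as much as the missing criterion. It does not settle the matter, because the plan does not choose that analysis.

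Other points have some force:

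- Youth in general complete relationship questions about a close friend, and the sentence on choosing a friend is not limited to the friend conditions. Most targets may well have one. The other family's permission and consent, however, matter only in the friend conditions.
- The investigators report past success with children bringing a best friend. They give no failure rate, so the higher values in the table have no documentary support.
- Relationship quality and the HBQ peer scales may enter as covariates, but only if group differences are found. With 50 per arm a moderate imbalance can be missed, and neither measures whether the friend's family agreed.
- The biases are below the roughly 0.56 SD detectable in one 50 versus 50 contrast (80% power, two-sided 5%). They still raise the false-positive rate.

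Three stronger readings are tempting and not supported. First, a reader might infer that friend-arm failures are lost or replaced while No Partner simply keeps an unfiltered sample. The only stated consequence of failed friend consent is conversion; the replacement in 10.1 concerns attrition and incomplete data. So *q* × *g* describes the Unfamiliar Peer contrast and not the No Partner one. Second, a reader might think that each replaced target also uses up an extra partner from the 50 spare places (400 − 350). No partner would have been enrolled for a target whose friend was never obtained. Third, the requirement should not be called a filter on sociability: it also reflects the other family's willingness and plain logistics.

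**Conclusion.** The concern stands as a design weakness that should be corrected. Friend availability is not required before assignment, it acts in two of four conditions, and the handling of conversions in the analysis is unstated. If sessions are analysed as tested, under an assumed 10% to 20% failure and a 0.5 SD difference, the spurious friend effect is about 0.05 to 0.10 SD against Unfamiliar Peer and 0.13 to 0.21 SD against No Partner. At 5% failure it is small: 0.025 and 0.07 SD.

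Both inputs, and the direction of the difference, are assumptions. The timing of the requirement is inferred. The calculation also applies conversion to every failure, although the rule is worded around consent and does not say what happens to a youth who can name nobody. With equal failure in both friend arms, the contrast between those two arms is not biased by this route. The documents do not show that bias has occurred; they show that nothing in the plan prevents it.

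**What to change.** - **8.1 and 8.3:** for every target, before randomisation, confirm that the youth can name a close same-sex friend within the partner age rule and that the friend's family agrees to be approached.
- **14.1:** randomise only after this is confirmed, whichever condition is then drawn.
- **14.3:** analyse any later friend failure or converted session in the condition assigned. This is needed because agreeing to be approached is not consent, so some failures will still follow assignment. Youth with no outcome fall under the missing-data methods in 14.4.
- **Reporting:** give friend failures, conversions and replacements by assigned arm, including for targets already enrolled, and state that conclusions apply to youth with an available close friend.

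Cost: one extra screening step for all families, somewhat slower recruitment in all arms, a narrower population, and some friends' families approached without being used. Targets to screen for 200 eligible are 200/(1 − *q*): 211 at 5%, 223 at 10%, 250 at 20%. Section 22.1 counts 14,529 + 15,284 = 29,813 children on the registry, so the extra screening looks affordable.

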
1.0 Objectives

1.1 Purpose: The purpose of this experiment is to determine whether social buffering by friends of stress physiology remains effective later in puberty when friends share the load versus when they provide support but are not undergoing the stressor with the target child. There are four conditions: (1) Friend and Target both undergo the stressor, (2) Friend provides support but does not undergo the stressor, (3) Unfamiliar Peer and Target undergo the stressor, and (4) Alone (no partner).

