become part of a group. Satisfying this need with high quality friendships positively predicts adult health (Allen, Uchino, & Hafen, 2015). From an evolutionary perspective, being with others has tremendous threat-protection value, and may be our baseline state (Beckes & Coan, 2011). While a teen might take a friend with her as received support when getting her ears pierced, it is also very common for youth to experience stressors in a group or with their friends who are going through the same stressful experience. During high-stakes exams or while walking school hallways where older kids are making fun of younger kids, it is intuitive that being with a friend helps make those situations less stressful. But, the friend is not only there as a support figure. Instead, both friends are giving AND receiving support from one another in these situations. We will examine a social evaluative stressor under four between group conditions: (1) two friends both experiencing the stressor, (2) two unfamiliar peers both experiencing the stressor, (3) one recipient and one giver of social support, and (4) one individual experiencing the stressor with no social support. *We predict that when two friends are in it together, being both recipients and givers of support, being with a friend will reduce physiological stress responding. However, when one friend gives support and the other receives it, the friend's presence will increase stress responding (as in our previous study, (Doom et al., 2016).*

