Stressor Paradigm: TSST paradigm with the child facing a camera and two judges (one male, one female). After consent, parents are invited to exit the call (or leave the room); in our recent experience with a Zoom'd TSST, youth and parents readily agreed to this separation. A period of 'rest' begins where youth watch approximately 20-25 minutes of a mildly amusing child appropriate animated movie. The experimenter then sends them to a breakout room to begin the TSST sequence. They are greeted by 2 "judges", given instructions for the speech and told that they have 5 min to prepare. During that time, the judges turn off their audio/video but clearly remain in the breakout room. When 5 minutes elapse, the judges reappear. If the condition is one of support, the Peer or Friend is sent back to the main room and either released from the call or told to continue preparation for another 10 minutes until it is their turn. The judges give final speech instructions, and tell the youth to begin their speech, and then transition to the math. That participant is then excused back to the main room. If the condition calls for a Peer or Friend to perform the TSST, they are then sent to the judging breakout room and deliver their speech/math. After each participant completes the speech/math, they return to the main room and are greeted by the friendly experimenter, who guides them through REDCap links to the various surveys. At several points in session 2, saliva samples are obtained.

Note: In all conditions, one participant will be the target, even though in two of the conditions (Close Friends and Unfamiliar Peer Both Tested), both youth will go through the TSST and all physiological measures will be obtained. The reason for this is two-fold: (1) when we recruit we will know

PROTOCOL TITLE: Does Social Buffering Continue to be Effective Over the Peripubertal Period
When Friends Share the Stressor Experience?

VERSION DATE: v.3.3 3.31.23

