MacArthur Health and Behavior Questionnaire (HBQ) for 9-18 Year-Olds (Parent and Child, 2.1): This questionnaire was developed by Marilyn Essex based on the original HBQ for 4-8 year olds. We have used it many times. The scales we proposed to use here have high reliabilities (Cronbach

PROTOCOL TITLE: Does Social Buffering Continue to be Effective Over the Peripubertal Period
When Friends Share the Stressor Experience?

VERSION DATE: v.3.3 3.31.23

alpha's > .8). We will use the peer scales (acceptance/rejection, bullied, relational victimization, asocial, behavioral inhibition) and broad-band symptoms scales (Internalizing, Externalizing). These measures will be examined for balance across groups and if differences by condition, pubertal stage, or sex are found, will be entered as covariates.

Self-Report of Stress: As a manipulation check, participants will rate their arousal and emotional state at various points during each study using Likert-type scales

Version 2.0 addition: Added Child-self-report RSQ for Peer, Family, & Academic Stress, and PALS Student report of adaptation to challenge in environment.

Physiological Measures.

Stress Hormones: We will assay saliva samples for stress sensitive hormones: **cortisol** and **alpha-amylase**. Saliva will be collected using SalivaBio Oral Swabs (SOS) or passive drool and stored frozen at -30°C until shipped for assay. All testing will be conducted in the late afternoon to control for circadian rhythm. Medications will be recorded from parent report and classes of drug codes will be used to group meds by presumed mechanisms of action and will be entered as covariates (Granger et al., 2009). Systemic glucocorticoid medications are an exclusion criterion. For each analyte, we will calculate area under the curve from intercept (AUCi) to provide a single measure for the main analysis.

- 5.3 Study Duration: Participants will attend two sessions. Session 1 will be 1-1.5hr; Session 2 will be 2-2.5 hrs. It is expected that it will take approximately 2 years to enroll all study participants, and that the study will end, including data analyses, approximately 5 years after enrollment begins.

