14.3 Statistical Analysis: The primary analyses will consist of a series of multiple regression models. For each dependent variable, Cortisol AUCi, Alpha-Amylase AUCi, we will begin by testing the three-way interaction between social buffering condition, sex, and pubertal stage for all outcomes. If the three-way interaction is not significant, we will then examine all two-way interactions. If the two-way interactions are not significant, we will then examine main effects only models. If the three-way interaction is significant, we will not examine any other model.

14.4 Data Integrity: *Multiplicity of testing.* We will correct for multiple comparisons using the Benjamini-Hochberg (BH) correction. The BH method works by controlling the false discovery rate, and relative to the Bonferroni's correction is more powerful, while still adequately protecting against Type I errors (Williams et al., 1999).

Missing data. If there is missingness in any of the dependent or independent variables, multiple imputation will be used (Little & Rubin, 2014; Peng et al., 2006; Schafer & Graham, 2002). Variables related to the missingness and the variables missing data will be included in the missing data model. In the event that missingness is not at random (MNAR), we will investigate the use of models for non-ignorable missing data.

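### Do the two primary AUCi outcomes need a stated baseline sample and window because the arms differ in who stays on the call?

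*Combined protocol and SAP*

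**What the plan says.** Section 3.2 names salivary cortisol and salivary alpha-amylase as primary. Section 5.2 (Stress Hormones) gives the summary: "For each analyte, we will calculate area under the curve from intercept (AUCi) to provide a single measure for the main analysis". Section 14.3 carries both into the models: "For each dependent variable, Cortisol AUCi, Alpha-Amylase AUCi, we will begin by testing the three-way interaction". On sampling, section 5.2 (Stressor Paradigm) says only: "At several points in session 2, saliva samples are obtained".

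The same part of 5.2 sets out the sequence. When the 5-minute preparation ends, the partner goes to the main room and is "either released from the call or told to continue preparation for another 10 minutes until it is their turn". The target then does the speech and math and goes back to the main room, and a tested partner takes a turn. "After each participant completes the speech/math, they return to the main room and are greeted by the friendly experimenter", who guides them to surveys. Section 5.1 adds that partners "who complete the TSST will undergo the same procedures as the Target Child during session 2".

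Section 1.1 asks whether buffering survives later in puberty "when friends share the load versus when they provide support but are not undergoing the stressor with the target child". Section 2.3 predicts that "when two friends are in it together, being both recipients and givers of support, being with a friend will reduce physiological stress responding", and the opposite when one friend only gives support.

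**The concern.** An AUCi depends on which sample is the intercept and which sample closes the area. Neither is named, session 2 lasts 2–2.5 hours, and a 20–25 minute rest precedes the task, so several definitions are open.

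This matters more here than in a trial whose arms run alike. A supporting friend is not tested, so the option of leaving the call can only be theirs. A tested friend stays and ends up in the same main room as the target. If the window runs past that point, a lower AUCi in the friends-both-tested arm could reflect having the friend on the call afterwards rather than sharing the stressor, which is the contrast section 1.1 asks about. In addition, a definition chosen after seeing results would count once in the Benjamini-Hochberg correction of section 14.4 although several had been available.

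**Working it through.** The documents state no figure that depends on the window, so there is nothing to reproduce. The steps below show how far the concern reaches and what it rests on.

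**1. Timeline.** Minute 0 is the start of preparation.

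- Preparation: 0–5 (section 5.2).
- Target's speech and math: about 5–15, inferred from the partner's further 10 minutes of preparation.
- Partner's turn: about 15–25, assumed to last as long as the target's.

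The target always goes first, so the target's own timing is the same in all four arms and one sampling clock can serve them all.

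**2. Share of the window after the partner's return.** With baseline at B and last sample at E, the share is (E − 25)/(E − B). The values of E are assumptions. B = 0 is a sample at the start of preparation; B = −25 is a sample before the rest period.

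| E (min) | B = 0 | B = −25 |
|---|---|---|
| 25 | 0/25 = 0% | 0/50 = 0% |
| 45 | 20/45 = 44% | 20/70 = 29% |
| 65 | 40/65 = 62% | 40/90 = 44% |
| 85 | 60/85 = 71% | 60/110 = 55% |

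**3. A purely hypothetical effect of later company.** Assume samples at −25, 0, 15, 25, 45, 65 and 85 minutes, equal variances, and correlation ρ^(lag/20). Let the two friend arms be identical up to minute 25 and then differ by δ SD at every later sample. AUCi is the trapezoid area minus baseline × window length. The trapezoid weights on samples after minute 25 sum to 10, 30 and 50 for E = 45, 65 and 85. The standardised difference is d = δ × (sum of weights)/SD(AUCi). With 50 v 50 the noncentrality is d × √(50/2) = 5d, tested two-sided at .05.

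- Highest case with B = 0 (ρ = .9, δ = 0.5): SD(AUCi) = 16.8, 28.9, 42.6, so d = 5/16.8 = 0.30, 15/28.9 = 0.52, 25/42.6 = 0.59. Chance of significance: 31%, 73%, 83%.
- Lowest case with B = 0 (ρ = .5, δ = 0.3): SD(AUCi) = 34.7, 55.4, 76.4, so d = 3/34.7 = 0.09, 9/55.4 = 0.16, 15/76.4 = 0.20. Chance of significance: 7%, 13%, 16%.
- With B = −25 the same two cases give 12%, 36%, 52% and 6%, 9%, 11%.

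The baseline alone moves the top figure from 83% to 52%. The shift δ has no source in the documents. Nor is an unadjusted 50 v 50 contrast the planned test: section 14.3 starts from the three-way interaction.

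**4. Choosing among definitions.** Under the null (20,000 simulated trials per ρ, N = 200, four arms, one-way 3-df F test), the smallest p of six definitions (two baselines × three window ends) is below .05 in 12–13% of trials. The smallest of the three window ends with B = 0 gives about 7%, and one definition about 5%. Most of the excess therefore comes from also varying the baseline, which has nothing to do with the partner's return. All of it presumes that six definitions are tried, whereas section 5.2 commits to one measure per analyte.

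**5. Would cutting the window at the partner's return help?** It would remove time after minute 25 only. From minute 5 a supporting friend may already have left the call while a tested friend waits and then performs, so the friend arms would still differ within the shortened window. The cut also needs a sample between the end of the target's task and the partner's return, about minutes 15–25, and the documents do not say that one exists.

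**The case for a change.** The strongest case for a change is that the primary outcome cannot be computed from the text alone. Sections 14.1 and 14.2 send the reader to a section 4.3 on outcome variables, but 4.3 in this document is the biosafety entry. Section 2.3 itself stresses that only the preparation period separates emotional from physical autonomic activity, and a single AUCi with no stated window does not show how that is respected. Writing down the sample times would cost a few lines.

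All of that stands as a description of missing detail. It does not show a wrong result. Section 5.2 has each returning youth guided through surveys, and nothing in the documents says that target and partner talk or see each other then. Section 2.3 describes the shared condition as friends who support each other through the same experience, so company afterwards may belong to the condition rather than contaminate it. The reference to a missing section 4.3 suggests that the definition was written elsewhere, although the supplied text cannot confirm this.

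**Conclusion.** No change to the plan is called for. The gap is real but ordinary: the analysts must name an intercept sample and a last sample before they can compute either outcome. Provided they use the same ones for each analyte in every arm, and settle them before looking at results by condition, the randomised comparison is unbiased whichever they choose.

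What remains is interpretation. With a long window, the contrast between a friend who shares the stressor and one who only supports includes whatever differs in company afterwards. That is between 29% and 71% of the window for ends of 45 to 85 minutes, on an assumed 10-minute partner turn and assumed sample times. A reader of the results can weigh this. The chances of 6–83% and the 12–13% false-positive rate illustrate invented inputs and are not properties of this trial. The one concrete alternative, an AUCi stopped at the partner's return, offers no demonstrated gain: it may lack a sample to end on, and it leaves the friend arms unlike each other from the end of preparation.
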